The registry will be implemented following the granting of the marketing authorisation for IV zanamivir and before the start of the first northern hemisphere influenza season following that grant. The registry will be opened in countries within the European Union (EU), United Kingdom (UK), Norway and Iceland. At present 100-150 exposures during pregnancy to IV zanamivir are proposed to be sufficient to detect 2-4-fold increases in the risk of adverse pregnancy outcomes of interest and therefore sufficient to detect a signal for substantial increase in risk. The prevalence of exposure to IV zanamivir is likely to vary across influenza seasons influenced by factors such as the underlying pathogenicity and resistance profiles of circulating virus strains. Accordingly, an update report will be filed with the EMA each year, providing details of the number of treated patients enrolled and guidance on the likely study end date.

Amendment or update no.	Date	Section of study protocol	Amendment or update
1	23-JUN- 2020	8.4 Data source 8.7 Data Analysis, sub- section Analysis Population	Clarified that additional de-identified data, collected by HCPs to supplement the primary analysis population collected through the pregnancy study, can include the minimal dataset collected under informed consent waiver from the UKOSS/INOSS network. This will enable access to a minimal set of data on women exposed to IV zanamivir from UKOSS/INOSS but who do not consent to participate in the current study.

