8.5. Study size

The effect sizes that are expected to be detectable were calculated. The effect size is defined as the ratio of the prevalence in exposed patients, estimated from the study, to the prevalence in the reference population. These calculations were performed using a binomial distribution, a power of 80% and a 1-sided Type 1 (false positive) error rate of 5% [Altman, 1991]. Assuming prevalence values in the reference population of 2% (MCMs) and 7.6% (preterm births), 100 exposed live births will be sufficient to detect a 4-fold increase in the risk of MCMs and a 2-fold increase in the risk of pre-term birth, relative to the reference-population prevalence. The calculations were performed using the software PASS (Version 12.0.2, copyright 1983-2013, NCSS, LCC).

Table 1Detectable effect size assuming 80% power

Sample size of live births (N)	PTB reference 7.6% ¹	LBW reference 7.0% ¹	MCM reference 2.00% ²
5	6.45	7.00	24.51
20	4.12	3.69	10.10
50	2.61	2.83	5.38
100	2.05	2.07	3.90
150	1.85	1.91	2.99

Abbreviations: LBW = low birth weight; MCM = major congenital malformations; PTB = preterm birth. ¹Prevalence from Office for National Statistics, 2015 ²Prevalence from EUROCAT, 2017

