Retrospective reports include subjects for whom the pregnancy outcome has already occurred. Retrospective reports can be biased toward the reporting of more unusual and severe cases and are less likely to be representative of the general population experience than exposures reported prior to knowledge of outcome. Although the exposure can be identified objectives through the UKOSS/INOSS systems, there is still the potential for bias to be introduced if there are delays in the women consenting and between exposure and consent there is additional knowledge of the outcome of the pregnancy. Where possible, the characteristics of prospective and retrospective reports will be compared to assess potential bias. If there is adequate evidence to support lack of bias these prospective and retrospective reports may be combined for analysis, but the initial analysis position will be for retrospective reports with reported MCMs and/or SABs will be reviewed to aid in detection of early signals and listed in registry reports.

Loss to Follow-up

For a prospective report of pregnancy where follow-up information on the pregnancy outcome (live birth, SAB, etc.) is never obtained or is unavailable, the pregnancy will be considered lost to follow-up. Subjects lost prior to pregnancy outcome will be tallied in the registry reports but not included in the statistical analyses.

Duplicate Registry Reports

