8.9.1. Study closure/uninterpretability of results

The prevalence of exposure to IV zanamivir is likely to vary across influenza seasons influenced by factors such as the underlying pathogenicity and resistance profiles of circulating virus strains. Accordingly, an update report will be filed with the EMA each year, providing details of the number of treated patients enrolled and guidance on the likely study end date. This will be used to inform on a more realistic study end date. At present 100-150 IV zanamivir exposures are proposed to be sufficient to detect a 2-4-fold

increase in pregnancy outcomes of interest therefore detecting a signal of substantial increase in risk.

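### The 2-4-fold detection claim was derived for 100-150 live births but is stated for 100-150 exposures; at the lower end it fails for preterm birth and low birth weight

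*Protocol*

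**What the plan says.** Section 8.5 calculates detectable effects with a one-sample binomial test, one-sided 5% error and 80% power. The sample size column of Table 1 is in live births. The text concludes that "100 exposed live births will be sufficient to detect a 4-fold increase in the risk of MCMs and a 2-fold increase" in preterm birth. The Table 1 entries at 100 live births are 2.05 (preterm birth), 2.07 (low birth weight, LBW) and 3.90 (major congenital malformation, MCM).

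The milestones part of the abstract uses a different unit: "100-150 exposures during pregnancy to IV zanamivir are proposed to be sufficient to detect 2-4-fold increases". Section 8.9.1, on study closure, does the same: "At present 100-150 IV zanamivir exposures are proposed to be sufficient to detect a 2-4-fold" increase. In both places the yearly report to the EMA that guides the end date gives the number of treated patients enrolled.

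Section 8.7 then limits who is analysed. On loss to follow-up: "Subjects lost prior to pregnancy outcome will be tallied in the registry reports but not included in the statistical analyses". Retrospective reports are at first analysed separately, invalid reports are left out, and section 8.7.1 excludes pregnancies exposed to major teratogens. The same section uses live births as the denominator for preterm birth, small for gestational age and LBW, and live births plus foetal losses with an MCM for MCM prevalence. Each infant of a multiple gestation counts.

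**The concern.** The number of exposures and the number of live births in the primary analysis are different quantities, and by the protocol's own rules the second will usually be smaller. Spontaneous abortion, induced abortion and stillbirth are listed outcomes. Section 6.1 itself cites raised foetal and perinatal death with influenza. Yet the same 100-150 and the same 2-4-fold appear against both units, with no allowance for the difference.

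The stake is how a null result is read. If the registry ended near 100 exposures, the protocol would support saying that it could have detected a doubling of preterm birth or LBW with 80% power, when the actual power could be well below that.

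**Working it through.** **Inputs.** From section 8.5: reference prevalences p0 of 7.6% (preterm birth), 7.0% (LBW) and 2.0% (MCM); one-sided 5%; 80% power; binomial distribution. From section 8.9.1: 100-150 exposures and 2-4-fold. The number of analysed live births per exposure is not in the protocol, so it is varied below as an assumption.

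**Method.** For N live births, take the smallest r with P(X ≥ r | N, p0) ≤ 0.05. The detectable ratio is p1/p0, where p1 solves P(X ≥ r | N, p1) = 0.80. Power for a k-fold increase is P(X ≥ r | N, k·p0).

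**Reproducing Table 1.** At N = 100, r is 13, 12 and 6, and the ratios are 2.05, 2.07 and 3.90, as printed. All 15 cells reproduce to within 0.01. A normal approximation (1.97, 2.02, 3.18 at N = 100) does not reproduce the table, so the exact test is the method used. Table 1 is correct for live births.

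**The same method at other counts.**

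| Live births analysed | r (preterm / LBW / MCM) | Detectable ratio at 80% power | Power at 2-fold / 2-fold / 4-fold |
|---|---|---|---|
| 70 | 10 / 10 / 5 | 2.29 / 2.49 / 4.71 | 64% / 52.5% / 67% |
| 80 | 11 / 11 / 5 | 2.19 / 2.38 / 4.13 | 69% / 57% / 78% |
| 90 | 12 / 11 / 5 | 2.11 / 2.12 / 3.68 | 73% / 73% / 86% |
| 100 | 13 / 12 / 6 | 2.05 / 2.07 / 3.90 | 77% / 76% / 82% |
| 105 | 14 / 13 / 6 | 2.09 / 2.12 / 3.71 | 74% / 72.5% / 85% |
| 120 | 15 / 14 / 6 | 1.95 / 1.99 / 3.25 | 83% / 80.5% / 92.5% |
| 150 | 18 / 17 / 7 | 1.85 / 1.91 / 2.99 | 89% / 86% / 96% |

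**Lower end, 100 exposures.** For preterm birth and LBW, no count from 50 to 100 live births gives 80% power at 2-fold. For these two outcomes the conclusion at 100 exposures therefore does not depend on the assumed yield, unless multiple births push the count above 100. How far power falls does depend on it.

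**MCM.** Power is not monotone in N because the exact cut-off falls from 6 to 5 events just below 100. Power at 4-fold is 90.5% at 99, 85.5% at 90 and at least 80% at every count from 83 to 99. It is below 80% at 70-82, a shortfall of 18% or more. It is at least 80% again at 68 and 69, where the cut-off drops to 4.

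**Upper end, 150 exposures.** A yield of 80% gives 150 × 0.80 = 120 live births, and all three parts of the claim hold. A yield of 70% gives 150 × 0.70 = 105, and the 2-fold part fails for preterm birth and LBW.

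**Exposures needed for 100 analysed live births**, 100/yield: 112 at 90%, 125 at 80%, 143 at 70%.

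**The case against.** The strongest reply is that nothing fixes a stop at 100. Section 8.9.1 presents the range as a current proposal, and yearly updates are meant to give a more realistic end date. A reader might infer that the registry will close at 100 exposures; the protocol does not say so, and section 5 sets no closing number. This bears on severity. It does not repair a sufficiency statement whose range includes 100.

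A reader might also infer that power is lost for malformations as soon as some exposures yield no live birth. The protocol's own method does not support this: a shortfall of up to 17% leaves 4-fold MCM power at 80% or more.

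The yield is assumed, and several features push it up. Section 8.7 expects most exposure after prenatal screening, hence after much early loss. Twins count twice. Retrospective reports may later be pooled if bias is judged absent. Reports that fail the minimum criteria may never be counted as enrolled. All of this stands, and at 90 live births the ratios (2.11, 2.12, 3.68) differ little from Table 1.

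Finally, the registry is descriptive, no decision depends on a power threshold, and confidence intervals will show the precision achieved. That limits the harm. The gap between 2.05 and 2-fold is rounding, visible in Table 1, and the 2-fold statement in section 8.5 concerns preterm birth only. It is a minor point.

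**Conclusion.** The unit mismatch is real, and the statement is wrong as written. At 100 exposures, 80% power for a 2-fold increase in preterm birth or LBW is not reached at any count from 50 to 100 live births. It is 77% and 76% with no loss at all, 73% for both at 90, and 69% and 57% at 80. MCM is affected only by larger attrition (70-82 live births). At 150 exposures the claim holds with 120 analysed live births and fails for preterm birth and LBW with 105. These figures rest on the protocol's reference prevalences and exact one-sided test; the yields of 70-90% are illustrative. This should be corrected, but it is not critical, because the registry is descriptive and the target is provisional.

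**What to change.** In the abstract milestones and section 8.9.1, state the target as live births in the primary analysis population (prospective, evaluable), and report that count in the yearly update beside the number of treated patients enrolled. Alternatively, keep the target in exposures, state an assumed yield, and give the detectable ratios for the resulting live births: for 100 exposures, about 2.19 / 2.38 / 4.13 (preterm birth / LBW / MCM) at 80% yield, or 2.29 / 2.49 / 4.71 at 70%.

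As a minor edit, in section 8.5 and the study size part of the abstract, write about 2.05-fold for preterm birth at 100 live births, or give 77% power for 2-fold.

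The cost is protocol wording and one extra count per yearly report. Recruitment procedures do not change. The stated sensitivity becomes slightly less favourable, or the number of exposures to be accrued somewhat larger.

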8.10. Other aspects

None.

9. **PROTECTION OF HUMAN SUBJECTS**

9.1. Ethical approval and subject consent

GSK respects the subjects' rights to privacy and will ensure the confidentiality of their medical information in accordance with applicable laws and regulations. Each patient's identity will be known only to the UKOSS/INOSS sites. The registry will assign patient and infant identification numbers, which will be used to identify registry participants and their infant offspring. The dataset used in each analysis of data from the registry will contain coded registry subject identifiers only for both the pregnant mothers and infants.

Each full-time and temporary employee involved with the registry from OXON, UKOSS and INOSS will be fully trained in the protection of human subjects and data privacy and follow established standard operating procedures (SOPs) that outline specifically how to maintain confidentiality and data protection of all registry participants. These SOPs also establish procedures to follow should privacy be compromised in any way. The research staff must be trained and tested on these privacy SOPs annually.

This study is designed and shall be implemented and reported in accordance with GPP, with applicable local regulations and with the ethical principles laid down in the Declaration of Helsinki. The protocol will be submitted for approval to applicable regulatory authorities and appropriate EC prior to registry implementation.

Eligible adults who wish to participate in the registry will be asked to provide informed consent for the collection of their data from their medical records and from the medical records of their infant after birth. Signed informed consent will be obtained in countries where it is required by local laws and regulations. In certain countries, the registry may qualify for verbal informed consent or waiver of documentation of signed informed consent (obtained by the process described below).

The registry will comply with local laws and regulations to facilitate release of participant and infant medical information to the registry.

9.2. Subject confidentiality

Each participant's identity will be known only to UKOSS/INOSS staff enrolling the individual (i.e., participant's HCP), and relevant HCPs (i.e. IV zanamivir prescriber, obstetrician, paediatrician and general practitioner). The registry will assign participant and infant identification numbers, which will be used to identify registry participants and their infant offspring. The dataset used in each analysis of data from the registry will contain coded registry participant identifiers only for both the pregnant women and infants.

10. LEGAL BASIS FOR PROCESSING INDIVIDUAL HUMAN DATA

The authors confirm that study data is Individual Human Data (IHD) owned by GSK and that:

- The proposed use of the IHD is **Study Use*** as outlined in the patient consent. **OR**
- The study IHD will be anonymised as described in STD_224418. **OR**
- The study IHD use is **Further Research** (as defined in SOP_52209 i.e. the use is anything other than Study Use*) **AND** the research participants consented to their IHD being processed for Further Research and have NOT submitted an Individual Rights Management (IRM) request that limits the use of their IHD.
- *Study Use means the use of IHD is as stated in the original study protocol and/or aligned with the informed consent form to answer the study objectives and satisfy regulatory requirements and learn more about the product studies and the disease/condition studied. This includes bringing the product to market or maintaining market access which includes working with government agencies, insurers or health care payers and aiding GSK's understanding of clinical efficacy, safety, or effectiveness of the product.

11. MANAGEMENT AND REPORTING OF ADVERSE EVENTS/ADVERSE REACTIONS

If, during the study, an adverse event (serious or non-serious) is identified as explicitly attributed to any GSK product (including products not covered in the specific study objective), this will be reported. The study epidemiologist or PV specialist at OXON must forward the report to GSK central safety department within 24 hours of first becoming aware of the event in accordance with SOP_54834 Management of Adverse Event, Pregnancy Exposure, and Incident Reports from Human Subject Research. The same process will be followed for pregnancy exposures or incidents related to any GSK product. On retrospective examination of patient records as part of the study operationalisation, these will also be collected by OXON for inclusion in the study report.

In addition, on retrospective examination of patient records as part of the study operationalisation, all adverse events (AEs) occurring during IV zanamivir exposure window, defined as from the start of treatment to 5 half-lives following the end of treatment, will be collected for inclusion in the study report. This will be equivalent to the collection of AEs between the time of start of treatment to 24 hours after the end of treatment. Due to the high levels of co-morbidities associated with the patient population of interest, AE collection in the mother is reserved to this specific observation period. In addition, adverse events of specific interest in the mother and infant, defined as study objectives and endpoints, will be collected during the study to meet study objectives.

This plan devised by OXON, in compliance with GSK requirement, will include the following elements to ensure a comprehensive approach to safety event collection and reporting:

- Supplier (OXON) pharmacovigilance training
- Investigator and site staff pharmacovigilance training (provided by OXON)
- Safety-specific roles
- AEs, pregnancy exposures, and incidents collection and reporting processes
- AEs, pregnancy exposure, and incident collection forms
- Frequency of data review
- Reporting process and timelines
- Interim reports
- Reconciliation process
- Study-specific PVP monitoring process
- Provision of final study report

The Strengthening the Reporting of Observational studies in Epidemiology (sPVP) or safety management plan will be developed prior to final protocol approval.

12. PLANS FOR DISSEMINATING AND COMMUNICATING STUDY RESULTS

12.1. Target Audience

The EMA, the Committee on Human Medicinal Products (CHMP) and the Pharmacovigilance Risk Assessment Committee (PRAC) will be the primary audience for this study. It will also be of interest to infectious diseases clinicians, obstetricians, paediatricians, teratology specialists, pregnant women and GSK stakeholders such as IV zanamivir project team members, and Global Safety Board. Additionally, this study will contribute novel data to the published literature.

12.2. Study reporting and publications

Key design elements of this registry will be posted in publicly accessible databases including, but not limited to, the European Union Post Authorisation Safety Study (EU PASS) Register. Furthermore, key results of this registry will be posted in publicly accessible databases within the required time-frame from completion of the data collection where applicable and in compliance with current regulations.

Annual updates and final reports will be generated which will be submitted to the relevant regulatory authorities.

The data may also be considered for reporting at scientific conferences or for publication in scientific journals. Preparation of such manuscripts will be prepared independently by

the SAC and in accordance with the current guidelines for STrengthening the Reporting of OBservational studies in Epidemiology [STROBE, 2009]. GSK will be entitled to view the results and interpretations included in the manuscript and provide comments prior to submission of the manuscript for publication.

13. **REFERENCES**

Altman, D.G. 1991. *Practical Statistics for Medical Research* (Chapman & Hall: London).

ANZIC Influenza Investigators and Australasian Maternity Outcomes Surveillance System. Critical illness due to 2009 A/H1N1 influenza in pregnant and postpartum women: population based cohort study. BMJ. 2010;340:c1279.

Briggs, G., R. Freeman, and S Yaffe. 2009. Drugs in Pregnancy and Lactation.

Correa-Villasenor, A., J. Cragan, J. Kucik, L. O'Leary, C. Siffel, and L. Williams. 2003. 'The Metropolitan Atlanta Congenital Defects Program: 35 years of birth defects surveillance at the Centers for Disease Control and Prevention', *Birth Defects Res A Clin Mol Teratol*, 67: 617-24.

Delgado-Rodriguez, M., J. Castilla, P. Godoy, V. Martin, N. Soldevila, J. Alonso,et.al.. Dominguez, Ciberesp Cases, and Group Controls in Pandemic Influenza Working. 2012. 'Prognosis of hospitalized patients with 2009 H1N1 influenza in Spain: influence of neuraminidase inhibitors', *J Antimicrob Chemother*, 67: 1739-45.

ANNEX 1: LIST OF STAND-ALONE DOCUMENTS

None
